The study Investigator and Coordinator will evaluate, characterize and record in the electronic Case Report Form (eCRF) all adverse events (AEs) occurring in all subjects from the time of enrollment to study exit (or premature withdrawal). Adverse events unresolved at study exit will be followed by the Investigator until resolution occurs or at least 30 days after the subject's participation in the study is complete. AEs may be reported spontaneously by the subject or detected by the Investigator or Coordinator. AEs should be evaluated for diagnoses not just symptoms (i.e., "angina", not "chest pain").

In addition to verbatim terms, the Sponsor may categorize all AEs using MedDRA preferred terms (PT) and system organ classes (SOC). Analysis may report both verbatim and MedDRA terms.

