16.5. Screening

Potential subjects will be screened for eligibility based on the criteria in Section 7 above. A potential subject who signs the study consent and is eligible will be assigned the same study ID number assigned to them during the RESTFUL Study, will be considered enrolled, and will count towards the study's sample size.

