16.15. Study Exit

Study exit will occur at the conclusion of Eval #9. At study exit, the Investigator/coordinator will complete the study exit eCRF. Adverse events unresolved at study exit will be followed by the Investigator until resolution occurs or at least 30 days after the subject's participation in the study is complete.

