3.2 Method of Assigning Subjects to Treatment

All subjects who are enrolled in Arm 1 will be assigned to:

- NTX100 programmed to ACTIVE mode for Weeks 1-24
- No treatment for Weeks 25-32

and will be instructed to maintain constant dosage and schedule of RLS medication (if applicable) for Week 1-32.

All subjects who are enrolled in Arm 2 will be assigned to:

• No treatment for Weeks 1-24 and will be permitted to change RLS medication during the study.

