6.3 Safety Analysis Population

The Safety Analysis Population will include all subjects enrolled. All analyses of adverse events will be based on this population.

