8.3 Safety Analyses

The proportion of subjects having one or more adverse events (AEs) between study entry and Week 24 will be presented by Arm. The proportion of subjects reporting AEs between Week 25 and Week 32 will be presented for Arm 1. Similar analyses will be done for serious adverse events (SAEs), device-related SAEs, and device-related AEs

Adverse events will be coded using the Medical Dictionary for Regulatory Activities (MedDRA). AEs will be summarized at the subject level using counts and percentages by MedDRA system organ class (SOC) and preferred term (PT). AEs will also be summarized at the event level using

counts and percentages by SOC/PT and seriousness, by SOC/PT and severity, and by SOC/PT and relationship to the device.

Frequency charts of adverse events occurring at any time during the study will be produced. The proportion of subjects with at least one AE will be presented overall and by SOC. The proportion of subjects with at least one occurrence of individual AEs will be presented for AEs occurring in >3% of subjects overall or within either Arm.

This document, when printed, is valid only until its new revision gets released, or when it becomes obsolete in the eQMS. The user of a printed copy of this document is responsible for using the current revision and for discarding superseded or obsolete revisions. The most current version of this document always resides in the eQMS.

Noctrix Health, Inc. CONFIDENTIAL CL-7 v2.0

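### The Arm 1 adverse-event proportion for Weeks 25-32 counts subjects who left before Week 25 as event-free, so it understates the risk among those followed by the share who left

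*SAP*

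**What the plan says.** SAP 8.3 plans two windowed AE proportions. The first runs from study entry to Week 24 and is presented by Arm. The second is for the off-device period: "The proportion of subjects reporting AEs between Week 25 and Week 32 will be presented for Arm 1". The same analyses are to be done for SAEs, device-related SAEs and device-related AEs. Neither sentence names a denominator.

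The denominator comes from the SAP's Safety Analysis Population section (the second of two sections numbered 6.3): "The Safety Analysis Population will include all subjects enrolled". Its scope is unrestricted: "All analyses of adverse events will be based on this population". Under Protocol 16.5, a subject who signs consent and is eligible "will be considered enrolled, and will count towards the study's sample size", so the status is fixed at entry.

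SAP 3.2 assigns Arm 1 "No treatment for Weeks 25-32". Protocol 16.15 places the planned end of participation at Week 32: "Study exit will occur at the conclusion of Eval #9". Protocol section 10 has AEs recorded as "occurring in all subjects from the time of enrollment to study exit (or premature withdrawal"). Protocol 16.16 lists reasons for removal before completion, among them an AE, withdrawn consent, non-compliance or loss to follow-up, pregnancy, a medication change and insufficient device supply.

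**The concern.** A proportion for a time window should be taken over people who could have had an event recorded in that window. Someone who leaves Arm 1 at Week 8 or Week 16 has no AE recording in Weeks 25-32. Under the SAP's population rule that person still sits in the denominator and adds a zero that was never observed.

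The presented figure therefore falls with each early exit, whatever happens to the subjects who are followed. Protocol 16.1 includes the eight weeks without the device in order to see what happens after treatment stops, and this is the only AE summary specific to that period. A reader would take it as the AE risk after stopping, and it would be too low for that purpose. The three companion proportions have the same defect.

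**Working it through.** **Inputs from the documents**
- Numerator: Arm 1 subjects reporting an AE in Weeks 25-32 (SAP 8.3).
- Denominator: all enrolled Arm 1 subjects (SAP Safety Analysis Population section, applied to SAP 8.3).
- End of AE recording: study exit or premature withdrawal (Protocol section 10).
- Exit before Week 25: foreseen in Protocol 16.16. Under 16.16.1, supply-related removal happens at a device replacement timepoint, which 16.13 typically puts at Eval 4 (Week 8) or Eval 6 (Week 16).

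The documents give no sample size (SAP 3.4 states that none was determined), dropout rate or AE rate, so there is no planned figure to reproduce. The rates below are assumptions.

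**Formula**
Let N be the number enrolled in Arm 1, d the share who left before Week 25, and r the Weeks 25-32 risk among those still followed.
- Expected number with an event recorded: r × N(1-d).
- Presented proportion: r × N(1-d) / N = r(1-d).
- Relative shortfall against those followed: 1 - r(1-d)/r = d.
- Absolute shortfall: r × d.

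**Size at an assumed r = 15%**

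| d | Presented r(1-d) | Shortfall in points |
|---|---|---|
| 0% | 15.0% | 0 |
| 5% | 0.15 × 0.95 = 14.3% | 0.75 |
| 10% | 0.15 × 0.90 = 13.5% | 1.5 |
| 20% | 0.15 × 0.80 = 12.0% | 3.0 |
| 25% | 0.15 × 0.75 = 11.3% | 3.75 |

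In counts, with assumed N = 100, 20 early exits and 8 subjects with an AE: 8/100 = 8.0% as planned, against 8/80 = 10.0% among those followed.

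**If the target is the whole enrolled cohort**
Let k be the leavers' unobserved risk divided by the stayers' risk. The cohort risk is r(1-d) + k·r·d, so the relative shortfall is 1 - (1-d)/[(1-d) + k·d]. At d = 20%:
- k = 0: 1 - 0.8/0.8 = 0%
- k = 0.5: 1 - 0.8/0.9 = 11%
- k = 1: 1 - 0.8/1.0 = 20%
- k = 2: 1 - 0.8/1.2 = 33%

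The shortfall equals d exactly only against the subjects followed, or for the whole cohort if k = 1.

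**Does post-exit reporting fill the gap?**
Protocol 10.3 covers SAEs that the investigator learns of within one month after the subject completes the study. Even if this is read to include early exits, a Week 16 exit reaches only about Week 20 (16 + 4), before the window opens. Follow-up of unresolved AEs after exit concerns events that had already begun. Neither adds new Weeks 25-32 events for someone who left at Week 8 or 16.

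**The case against.** The strongest objection is that SAP 8.3 names no denominator and the all-enrolled reading is an inference. The table shells in SAP Appendix A are not in the text available for this review, and an at-risk n in Table 4.1 cannot be ruled out. That uncertainty stands. However, the SAP body states its population rule for all AE analyses without exception, so a shell with a different n would contradict it, and the text would still need correcting.

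Off-device events are also not hidden. The AE frequency charts cover the whole study, the AE listing is by subject, and Arm 1 completion rates are to be presented (SAP 9.0). This is fair, but none of these gives a proportion for Weeks 25-32, and readers would have to rescale the figure themselves.

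The effect may also be small. At 10% attrition the shortfall is 1.5 points on 15%, while the standard error of a 15% proportion is about 5.0 points at an assumed N of 50 and 3.6 at 100. Protocol 16.16.1 calls a supply shortage unlikely. This limits the importance of the point, although the error is systematic and avoidable.

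Two stronger readings are tempting, and the documents support neither.
- **That the error favours the device.** It understates AEs after stopping, but by the same amount it makes the on-device period look worse by contrast. An AE that led to removal before Week 25 still counts in the entry-to-Week-24 proportion. The direction depends on the question asked.
- **That the 24-week and 8-week proportions are being compared unfairly.** Crude proportions over windows of different length are not on one scale: at a constant rate, an assumed 30% over 24 weeks corresponds to 1 - 0.70^(8/24) = 11.2% over 8 weeks. But the SAP plans no comparison between the windows and states the week range of each.

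**Conclusion.** The point holds as a defect in a stated rule. Read together, SAP 8.3 and the Safety Analysis Population section divide the four Weeks 25-32 proportions by all enrolled Arm 1 subjects, including any who left before the window opened. Relative to the subjects followed, each proportion is too low by the share who left.

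That relation is exact, but its numerical size here is unknown because it rests on dropout and AE rates that the documents do not give. The conclusion also assumes that the unseen table shells follow the SAP text. The protocol does not repair it: section 17.3.2 bases the safety analysis on all treated subjects, which is likewise not restricted to those followed past Week 24. The consequence is confined to one descriptive safety summary. No hypothesis test is affected, nor is the SAP's entry-to-Week-24 AE proportion. It is worth correcting before the tables are produced, but it does not threaten the study's main conclusions.

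**What to change.** In SAP 8.3, define the denominator for all Weeks 25-32 proportions (AEs, SAEs, device-related SAEs, device-related AEs) as enrolled Arm 1 subjects still in follow-up at the start of Week 25, and print that n in the table. State this exception in the Safety Analysis Population section, and check that the Table 4.1 shell agrees. Keep the all-enrolled denominator for study entry to Week 24. Events per subject-week of observed follow-up could be added beside each window, but this is optional.

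The cost is a few lines of SAP text and one extra n. Protocol section 10 already requires AE onset dates, and Protocol 16.15 and 16.16.1 require a study exit form. The documents do not list that form's fields, so confirm that it holds the exit date. There are two consequences to accept. The off-device figure will be higher whenever anyone has left early, and it will describe only those who remained in follow-up, so it does not recover the experience of those who left. Subjects who exit during Weeks 25-32 will still be only partly observed.

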- b. [Cohort 2B] There is a variable delay between RESTFUL Study completion and Arm 2 entry, depending on the time that the subject completed the Restful Study. Subjects will be enrolled either 8-wks, 16-wks, or 24-wks after completion of the RESTFUL Study, +/- 1-wk.

Completion

a. Both Cohorts 2A and 2B are completed 24-wks after completion of the RESTFUL Study
 +/- 1-week. Therefore, the duration of study participation in Arm 2 depends on the delay between RESTFUL Study completion and enrollment in this study.

Baseline

a. For both Cohorts 2A and 2B, baseline refers to RESTFUL Study entry (Eval 1 of Restful Study).

Table 3. Comparison of Study Arms

	Arm 1	Arm 2	Arm 3 Earlier cohort of RESTFUL Study subjects		
Eligibility	Later cohort of RESTFUL Study subjects	RESTFUL Study subjects who don't complete Arm 1			
Start date relative to RESTFUL Study completion	0* days	Less than 24-wks	Fixed delay, >=24-wks and <=52-wks		
End date relative to RESTFUL Study completion	32-wks	24-wks	Variable		
Duration	32-wks	up to 24-wks	32-wks		
Investigational device use	Wks 1-24	None	Wks 1-24		
Baseline	RESTFUL Study entry	RESTFUL Study entry	Entry to this study		

^{*} Up to 2 days if needed

Investigational Plan, Protocol CT-05 (Extension Study)

Document #: CT-4

Rev: 1.0

Effective: 11/24/2021

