3.1 Overview

Subjects who previously completed the RESTFUL Study [Protocol Number: CT-04; ClinicalTrials.gov Identifier: NCT04874155] consent to one of two Arms, the design of which is

illustrated in the flowchart below (Figure 1). Arm 1 is a Direct Roll-Over Extension and Arm 2 is a Control.

- **Arm 1** (Direct Roll-Over Extension) Arm 1 is only an option for subjects who successfully complete RESTFUL Study after enrollment to CT-05 begins at a given clinical site; Arm 1 involves a 24-wk extension period of NTX100 device use followed by an 8-wk period without device use. Subjects in Arm 1 are instructed to maintain constant dose and schedule of RLS medication (if applicable).
- Arm 2 (Control Group) Arm 2 is an option for subjects who successfully complete the RESTFUL Study before enrollment to CT-05 begins at a given clinical site or subjects who decline to participate in Arm 1. Subjects enrolled in Arm 2 will receive no treatment with the NTX100 device during Arm 2. Arm 2 involves assessment during the 24-wks after RESTFUL Study completion. Subjects in Arm 2 are permitted to change RLS medication.

Figure 1: Study Design Flowchart

The schedule of assessments for this study is presented in Table 1.

Table 1: Schedule of Assessments

	Eval 1			Eval 2	Eval 3	Eval 4	Eval 5	Eval 6	Eval 7	Eval 8	Eval 9	
	Day 0	Wks 1-24	Wks 25-32	Wk-2	Wk-4	Wk-8	Wk-12	Wk-16	Wk-20	Wk-24	Wk-32	
	In-person	Remote	Remote	Remote	Remote	In-person or Remote**			Remote	In-person	Remote	
Completed by												
	X											
	X											
Staff + subject	X											
Subject		X										
Subject			х									
Staff				X	X	x	X	x	X	X		
Staff	X			Х	Х	x	X	Х	Х	х	X	
Staff				X	Х	x	X	x	X	Х	X	
Staff + subject				Х	Х	x	Х	Х	Х	х	X	
Staff + subject				X	X	x	X	x	X	X	X	
Investigator + subject						х		х		Х	X	
Staff + subject					Х	x	X	Х	х	х	X	
Staff + subject	X									х		
Staff + subject										х		
Staff + subject											X	
Staff + subject	X **					X **		X **				
	* Data from Eval	11 of the RE	STFUL Study	will be us	ed, since b	oth Evals typic	cally occu	r on the same	day			
	Staff + subject Subject Subject Staff Staff Staff Staff Staff + subject Staff + subject Investigator + subject Staff + subject	In-person	Day 0 Wks 1-24 In-person	Day 0	Day 0 Wks 1-24 Wks 25-32 Wk-2	Day 0	Day 0	Day 0	Day 0	Day 0 Wks 1-24 Wks 25-32 Wk-2 Wk-4 Wk-8 Wk-12 Wk-16 Wk-20 In-person or In-pe	Day 0 Wks 1-24 Wks 25-32 Wk-2 Wk-4 Wks-4 Wks-12 Wk-16 Wk-20 Wk-24	Day 0

		Eval 1	Eval 2	Eval 3	Eval 4	

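### SAP 8.3 charts adverse events over the whole study (32 weeks in Arm 1, at most 24 in Arm 2) and states no window for the SOC/PT tables or the >3% display, so by-Arm cumulative figures may not be like-for-like

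*SAP*

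**What the plan says.** SAP 8.3 contains two groups of AE displays.

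The headline group has explicit windows. "The proportion of subjects having one or more adverse events (AEs) between study entry and Week 24 will be presented by Arm", and "The proportion of subjects reporting AEs between Week 25 and Week 32 will be presented for Arm 1". The section then adds: "Similar analyses will be done for serious adverse events (SAEs), device-related SAEs, and device-related AEs".

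The term-level group does not. For the charts the SAP says "Frequency charts of adverse events occurring at any time during the study will be produced"; Protocol 17.3.2 has the same sentence. The proportion with each individual AE "will be presented for AEs occurring in >3% of subjects overall or within either Arm". The subject-level SOC/PT summary and the event-level summaries by seriousness, severity and relationship state no window, and neither do the titles of Tables 4.2 to 4.5 in the SAP's list of tables.

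On follow-up, SAP 3.1 says Arm 1 "involves a 24-wk extension period of NTX100 device use followed by an 8-wk period without device use". For Arm 2, Protocol 16.2 says "Both Cohorts 2A and 2B are completed 24-wks after completion of the RESTFUL Study", within a week either way. Protocol Section 10 requires recording of all AEs "occurring in all subjects from the time of enrollment to study exit (or premature withdrawal").

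**The concern.** The term-level displays are where a reader looks to see which events occur more often with the device than without it. The reference to either Arm in the >3% rule shows that such a comparison is intended. If Arm 1 is counted over 32 weeks and Arm 2 over 24 or fewer, Arm 1 can show a higher cumulative proportion with no difference in underlying risk. Some terms could pass the 3% cut only because Arm 1 is watched for longer.

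An Arm 1 figure for Weeks 0 to 32 also describes neither the period on the device nor the period after stopping it. Protocol 16.1 gives the 8 weeks their own purpose, which is to follow RLS after treatment ends, so events in that period deserve their own display.

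**Working it through.** **1. Follow-up by Arm.** Arm 1 is 24 + 8 = 32 weeks, which reproduces the 32 weeks in Protocol Table 3. Arm 2 is listed there as up to 24 weeks. The ratio is 32/24 = 1.33 for an Arm 2 subject with full follow-up, and 8/32 = 25% of Arm 1 observation time lies beyond the longest Arm 2 window (visit windows aside).

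**2. Window stated for each display in SAP 8.3.**

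| Display | Window stated |
|---|---|
| Any AE, SAE, device-related SAE, device-related AE | Entry to Week 24 by Arm; Weeks 25 to 32 separately for Arm 1 |
| Frequency charts | Whole study |
| SOC/PT summaries (Tables 4.2 to 4.5) | None |
| Individual AEs above 3% | None |

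Only the charts are expressly whole-study. For the last two rows a 32-week count in Arm 1 is an inference from the collection period.

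**3. Effect of the extra 8 weeks.** The documents give no AE rates, so the 24-week risks p24 below are assumptions. With the same constant hazard in both Arms, on and off device, p32 = 1 − (1 − p24)^(32/24).

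| Assumed p24 | p32 | Excess (points) |
|---|---|---|
| 10% | 1 − 0.90^(4/3) = 13.1% | 3.1 |
| 20% | 1 − 0.80^(4/3) = 25.7% | 5.7 |
| 30% | 1 − 0.70^(4/3) = 37.8% | 7.8 |
| 50% | 1 − 0.50^(4/3) = 60.3% | 10.3 |

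If a term cannot occur off device, its off-device hazard is zero, p32 = p24 and the excess is 0. For p24 = 20% the excess therefore runs from 0 to 5.7 points as the off-device hazard goes from nil to equal.

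**4. The 3% cut.** The 24-week risk that reaches 3% at 32 weeks under the same assumption is 1 − 0.97^(24/32) = 2.3%.

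**5. What a Week-24 cut leaves.** Protocol 16.2 lets Cohort 2B enter 8, 16 or 24 weeks after RESTFUL, which leaves about 24 − 8 = 16, 24 − 16 = 8 or 24 − 24 = 0 weeks. Take an assumed equal mix of 24, 16, 8 and 0 weeks (mean 12) and equal hazards:

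- p24 = 10%: Arm 2 shows (10.0 + 6.8 + 3.5 + 0)/4 = 5.1%, a gap of 10.0 − 5.1 = 4.9 points.
- p24 = 20%: Arm 2 shows 10.2%, a gap of 20.0 − 10.2 = 9.8 points.

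So the cut removes the 32-versus-24 mismatch but not the one from late Arm 2 entry. Protocol 16.12 times the last Arm 2 call from Eval 1, whereas 16.2 times it from RESTFUL completion. These must be reconciled. The Arm 2 maximum is about 24 weeks either way, but the shortfall of late entrants depends on the answer.

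**The case against.** The strongest reply is that little depends on these displays. The safety endpoint is descriptive, and SAP 8.3 defines no between-Arm test (SAP 5.1 only sets a general level for safety tests). The four headline summaries already separate the two periods, including device-related AEs, where the on/off-device distinction matters most. Extra follow-up can only add Arm 1 events and Arm 1 terms, so cumulative counts err against the device. The whole-study charts follow the protocol. The constant hazard is doubtful too: the anticipated observations in Protocol 9.1 are tied to wearing the device, its electrodes or active stimulation. Arm 1 also has only one scheduled AE contact after Week 24 (Eval 9), so fewer events may be captured then.

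Most of this stands, and it limits the severity and makes the figures in step 3 illustrative. It does not make the windows comparable. A descriptive display is still read across Arms, and a merged figure still hides when an event occurred.

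Three stronger readings are tempting, and the documents do not support them:

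- **That the SAP has Tables 4.2 to 4.5 count events over the whole study.** That wording is attached to the charts only. The table shells in the SAP's Appendix A are not in the text available and may set a window.
- **That the safety analysis as a whole mixes on-device and off-device events.** The headline proportions do not.
- **That Arm 1 AE rates are inflated.** Cumulative counts and proportions grow with follow-up. A rate per subject-week need not, and could fall if fewer events occur off device.

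**Conclusion.** The point holds in a limited form. The frequency charts as written, if shown by Arm, set up to 32 weeks in Arm 1 against at most 24 in Arm 2 and merge 24 on-device with 8 off-device weeks. The same applies to the SOC/PT tables and the >3% display if they use the full collection period, which the SAP text leaves open. The follow-up difference is firm, at a factor of 1.33 or more. Its effect on proportions is not known. The 3.1 and 5.7 points at assumed 24-week risks of 10% and 20% rest on a hazard that is equal between Arms and constant on and off device. No efficacy result or headline safety proportion is affected. This is a cheap improvement of low-to-moderate severity.

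**What to change.** In SAP 8.3:

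- State the window for every AE display. Base the by-Arm frequency charts, the >3% cut and Tables 4.2 to 4.5 on AEs with onset from study entry to Week 24.
- Show Arm 1 Weeks 25 to 32 by SOC/PT in a separate table or column, labelled as off device. This extends the split that the section already uses for the headline proportions.
- Give subject-weeks of observation and events per subject-week by Arm, because late Arm 2 entrants contribute less than 24 weeks.
- Record the change in SAP 3.5, since Protocol 17.3.2 specifies the whole-study charts. A whole-study chart may stay if its window and observation time are labelled.

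The cost is a few sentences, a filter on onset date (which Protocol Section 10 already has recorded), a person-time line and one extra table. The main charts will show fewer Arm 1 events. One difference remains and should be noted beside the tables: scheduled AE contacts through Week 24 number 7 in Arm 1 (Evals 2 to 8) and at most 3 in Arm 2 (Evals 2 to 4).
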